6.2. Subgroup Analyses of the Primary Endpoint

Subgroup analyses of the primary endpoint will be conducted for disease type (COPD, OHS, Neuromuscular disease, Other) and ventilator dependency (Dependent vs Non-Dependent). Descriptive statistics will be presented stratified by disease categories and ventilator dependency, including the sample size, mean, standard deviation, median and range of the paired differences in ODI4% comparing Auto and Manual EPAP.

7. Statistical Analysis of Secondary Objectives

Secondary endpoints include (1) the assessment of AHI as measure by the Astral device and (2) sleep-breathing parameters (e.g., nadir spO₂ and PtCO₂) and sleep parameters (e.g. sleep efficacy index and arousal index) comparing AutoEPAP algorithm to manual EPAP on an Astral Device. Descriptive statistics will be presented for AHI as measured using manual EPAP on the Astral device. Descriptive statistics will be presented separately for sleep-breathing and sleep parameters for AutoEPAP and manual EPAP, as well as for the paired differences comparing results for manual EPAP and AutoEPAP. Descriptive statistics include mean, standard deviation, median, median, inter-quartiles, minimum and maximum values.

8. Additional Analyses

Descriptive statistics of baseline characteristics for all study subjects will be generated. An analysis of comparability of baseline characteristics by study site will be done. Pseudo-sites as described in Section 3 will be used for this analysis. For continuous variables such as age, an analysis of variance or Kruskal-Wallis test will be done to determine if study site is a significant factor with the characteristic being evaluated as the dependent variable. For categorical variables like gender, a Fisher-Freeman Halton test will be used. If the P-value from an analysis is ≤ 0.10 , that variable will be considered unbalanced among the study sites and will be used in multivariable analyses of the poolability analysis if indicated.

Serious adverse events and events related to the Astral device will be tabulated for the Enrollment population, presenting the number of patients having one or more of each event and the associated percentage. A distinction will be made as to whether the subjects having adverse events were part of the ITT or Enrollment populations. In addition, a listing of these events will be presented, including the event description, time of occurrence, severity, outcome, action taken and relationship to the study device.

A separate listing of all other adverse events (non-serious and not related) occurring during the study period will be generated, including the event description, time of occurrence, severity, outcome, action taken and relationship to the study device.

9. Handling of Missing Values

The primary analysis will be based on the CC population. A multiple imputation sensitivity analysis will be done in the following way. Patients who dropout between the first and second PSG visit periods, will

have their second PSG visit data imputed, using the multiple imputation procedure MI in SAS. The imputation model will include randomization group and first period ODI4% as predictor variables. Results will be pooled using the MIANALYZE procedure in SAS.

10. Justification of Sample Size

Using a sample size calculation based on a normal distribution, the sample size required for 80% power to detect a difference in ODI of 1 event/hour, using a one-sided significance level of 0.05, was calculated to be 23 subjects assuming a SD of 1.55 in the Astral VAPS AutoEPAP Clinical Trial Protocol.

[Using the normal approximation formula for sample size as written in the protocol, I calculate a sample size of 15 patients required based on SD=1.55, beta=0.2, one-sided alpha=0.05, and a detection difference between groups of 1. Using a two-sided alpha of 0.05, the sample size is 19. Using PASS software (2) which uses the t distribution to calculate the sample size for paired means rather than the z distribution, the sample size is 17 for a one-sided alpha of 0.05, and 21 for a two-sided alpha of 0.05].

11. Protocol Deviations

Protocol deviations occurring during the study will be tabulated.

11. Statistical Software and Programming

The creation of analysis datasets and all statistical analyses will be generated using SAS version 9.3 or later. Graphics will be either generated using SAS software or R software. Good programming techniques including the use of sufficient program documentation, following naming conventions, good code structure, use of independent validation programs, and avoidance of hard coding will be practiced. All programming code will be independently peer-reviewed.

12. References

- (1) Meinert, C. (1986). *Clinical Trials: Design, Conduct, and Analysis*. Oxford University Press, New York.
- (2) Hintze, J. (2012). PASS 14. NCSS, LLC. Kaysville, Utah, USA. www.ncss.com
- (3) Guidance for Industry: E9 Statistical Principles for Clinical Trials. U. S. Department of Health and Human Services, Food and Drug Administration, Center for Drug Evaluation and Research and Center for Biologics Evaluation and Research. International Committee on Harmonization, September 1998.

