3. PROTOCOL SUMMARY

Objectives	The objective of this study is to evaluate AutoEPAP versus manual EPAP in iVAPS mode on the Astral device.
Study Design	This will be a prospective, multi-center, single-blind, randomized, cross-over design. The study will occur in a lab/hospital setting. Eligible subjects that represent patients with respiratory failure will complete two PSG study nights.
Number of Subjects	Up to 40 subjects overall will be randomized to obtain endpoint data on at least 36 evaluable subjects. This accounts for the expected dropout rate (10%).

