5.2. Secondary Objectives

The secondary objectives will be used to determine if the AutoEPAP algorithm remains effective in treating respiratory failure.

1. To assess the apnea hypopnea index (AHI) as measured by the Astral device.
2. To assess sleep-breathing parameters (e.g. nadir SpO₂ and PtCO₂) with AutoEPAP algorithm compared to manual EPAP on an Astral device.
3. To assess sleep parameters (e.g. sleep efficacy and arousal index) with AutoEPAP algorithm compared to manual EPAP on an Astral device.

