Ensure a new USB flash drive is labelled and inserted into the Astral device prior to the commencement of the study. The device's ID number is to be recorded in the CRF before the end of the visit. Ensure there is an SD card in the machine, and the SD card is labelled with the participant ID number, therapy type, Night 1.

Visit 1 and 2 may be conducted on the same day.

9.2.1. Visit 3

Participants will undergo an overnight PSG at the site per their randomized group assignment. Full PSG set-up, data acquisition, monitoring and reporting will be performed using the AASM 2007 criteria. Therapy will be delivered using the clinical trial device, Astral. At least 4 hours of recording will be required.

Participants' trial devices will be setup according to the therapy settings detailed in the Therapy section of this protocol. The set-up of manual EPAP or AutoEPAP settings shall occur before lights out. Study staff will also set up the subject to test PtCO₂. This may be done with a device clipped to the outside of the subject's ear, and does not introduce risk to the subject.

Ensure a new USB flash drive is labelled and inserted into the Astral device prior to the commencement of the study. The device's ID number is to be recorded in the CRF before the end of the visit. Ensure there is an SD card in the machine, and the SD card is labelled with the participant ID number, therapy type, Night 2.

The completion of Visit 3 marks the completion of study participation. Participants will return to their usual NIPPV therapy and have the option of keeping the mask and chinstrap that was used during the study.

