12. STATISTICAL ANALYSIS

Data recorded during 'Ramp' time (i.e. the time taken for the pressures to increase to the prescribed settings when the device is first turned on) will be excluded. Data will be checked for normality. If the data is normally distributed, descriptive data will be presented as mean and standard deviation (SD), and marginal differences. Comparisons between the two modes will be done using paired T-test.

If the data is not normally distributed, descriptive data will be presented as median and interquartile range (IQR). Comparative analysis between AutoEPAP and manual EPAP will be performed using the Mann-Whitney U test.

A $p < 0.05$ will be considered significantly different between AutoEPAP and manual EPAP if: 1. there is no significant difference between AutoEPAP and manual EPAP or 2. AutoEPAP is significantly better than manual EPAP, than the null hypothesis will be rejected and the AutoEPAP algorithm will be considered as 'passed'.

We pre-specify a non-inferiority margin for ODI4% of 2 per hour and specify a statistical test for non-inferiority as:

Non-inferiority margin for ODI: $d=2$

H0: $\mu_A - \mu_B \leq -d$ (new algorithm is inferior)

H1: $\mu_A - \mu_B > -d$ (new algorithm is non-inferior)

To show non-inferiority the lower bound of the 95th confidence interval of the difference between the groups must not cross the margin boundary (ODI4% of 2 per hour).

Which will be tested with a single-sided t-test with an alpha of 0.05 and a power of 80%. This pre-specified non-inferiority margin for ODI4% of 2 per hour is considered clinically unimportant, is the same margin as used in a previous study [26], and 2 per hour represents approximately 7% of severe UAO (30 per hour).

We also pre-specify that we will reject subjects where the ODI4% cannot be controlled during the control arm phase (manual EPAP). This is defined as an ODI ≥ 10 per hour. This process will be documented in the study Manual of Procedures and training provided for all participating sites.

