The primary endpoint analysis will be based on the CC subject population. A sensitivity analysis of the primary endpoint will be generated for the Enrollment population for patients who complete all study visits. An additional sensitivity analysis for the primary endpoint will be generated for the ITT population. The ITT population may contain some subjects who complete that first study PSG visit but not the second study PSG visit. This will require the use of imputation methods for missing values which are documented in Section 9.

All safety analyses will be generated for subjects in the Enrollment population. All secondary endpoints will be generated using the CC population.

3. Poolability analysis

The issue of poolability of the data entails two features: the combining of data across study sites and the method of computation of an overall estimate for study endpoints. The justification for combining of data across sites is based on the clinical assessment provided by Meinert (1): the clinical study will be conducted under a common protocol for each investigational site, the study sites will be monitored for protocol compliance, and the same data gathering instrument and method will be used in every site.

The justification for pooling all the data to estimate a common effect across study sites requires the homogeneity of response across study sites. An analysis of variance (ANOVA) of the differences will be generated to test whether the investigational sites differ with respect to primary study endpoint for the CC population (only the site will be included in this analysis model). The test of in homogeneity of response will be based on a two-sided significance test at the 0.15 level of significance. If the sites differ by this test, then a second analysis will be done including study site and all baseline characteristics that have $P < 0.10$ in

the analysis of baseline characteristics by site to understand if the imbalance in the primary endpoint between sites is related to an imbalance in baseline characteristics.

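### SAP section 7 summarises device-measured AHI under manual EPAP only, so the first secondary endpoint has no planned AutoEPAP value and no paired difference

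*SAP*

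**What the plan says.** Protocol section 5.2 gives the purpose of the secondary objectives: "The secondary objectives will be used to determine if the AutoEPAP algorithm remains effective in treating respiratory failure". The first objective is "To assess the apnea hypopnea index (AHI) as measured by the Astral device". It is not limited to one EPAP mode. Objectives 2 and 3 add an explicit comparison with manual EPAP; objective 1 does not.

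SAP section 7 keeps AHI apart from the rest. Device-measured AHI is item (1), and sleep-breathing and sleep parameters together form item (2). Each item then has its own analysis sentence. For AHI: "Descriptive statistics will be presented for AHI as measured using manual EPAP on the Astral device". For item (2): "Descriptive statistics will be presented separately for sleep-breathing and sleep parameters for AutoEPAP and manual EPAP, as well as for the paired differences".

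Two more general statements bear on the point. SAP section 2 fixes the analysis set: "All secondary endpoints will be generated using the CC population". Protocol section 12 says, without naming an endpoint: "Comparisons between the two modes will be done using paired T-test".

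**The concern.** The question behind the secondary objectives concerns AutoEPAP. A summary of AHI under manual EPAP describes the control condition and cannot answer it: the one mode that SAP section 7 tabulates is the one the question is not about.

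AHI is also not an incidental variable here. Protocol section 4.1 explains that AHI cannot be scored from the sleep-study recording with this ventilator and that ODI4% stands in for it. Device-measured AHI is thus the only AHI named as an endpoint. The same section reports the earlier AutoEPAP trial as mean AHI in both modes (1.7 per hour with manual EPAP, 1.3 per hour with AutoEPAP). The present SAP, as written, would not produce a two-mode display of that kind.

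The practical risk is that AutoEPAP AHI is either left out of the report or added outside the written SAP, where it can look like a choice made after seeing the data.

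**Working it through.** This is a check of text; no power or error-rate figure is involved.

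**Step 1. Planned summaries for each secondary endpoint in SAP section 7.**

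| Endpoint | AutoEPAP | Manual EPAP | Paired difference |
|---|---|---|---|
| (1) Device-measured AHI | not planned | planned | not planned |
| (2) Sleep-breathing parameters | planned | planned | planned |
| (2) Sleep parameters | planned | planned | planned |

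AHI receives 1 of 3 summaries; the others receive 3 of 3.

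**Step 2. Does another part of the SAP fill the gap?** Section 2 sets the population for secondary endpoints but no summaries. Section 4 lists generic statistics for continuous variables without saying which variables or modes. Section 6, including the subgroup analyses in 6.2, covers ODI4% only. Section 8 covers baseline characteristics and adverse events. Section 9 covers imputation of second-night data for the sensitivity analysis of the primary endpoint. None of them mentions AHI.

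**Step 3. Does the protocol fill it?** Section 5.2 makes AHI an objective but plans no analysis. Section 12 compares the two modes in general terms without naming AHI. The SAP is the later and more specific text, and for AHI it names manual EPAP alone.

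**Step 4. Extent.** Protocol section 3 states: "Up to 40 subjects overall will be randomized to obtain endpoint data on at least 36 evaluable subjects". Each subject has two study nights, one per mode.

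- 36 evaluable subjects: 36 × 2 = 72 nights. AutoEPAP nights with no planned AHI summary: 36, and 36/72 = 50%. Paired differences planned: 0 of 36.
- If all 40 complete: 40 × 2 = 80 nights. AutoEPAP nights with no planned AHI summary: 40, and 40/80 = 50%. Paired differences planned: 0 of 40.

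These counts only restate that one of two modes is missing. They do not measure bias or loss of power.

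**Step 5. Would the data exist?** Protocol sections 9.2 and 9.2.1 give the same instruction for both nights: "Ensure a new USB flash drive is labelled and inserted into the Astral device prior to the commencement of the study". Section 13.1 lists the flash drives among the raw data sources. This suggests that device data are captured in both modes. No section states what the drive records, or that AHI is logged under AutoEPAP.

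**The case against.** The best defence has four parts.

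- **Objective 1 promises no comparison.** Unlike objectives 2 and 3, it does not mention manual EPAP as comparator, so omitting a paired difference breaks no explicit commitment. This stands, and it makes the paired difference the weaker half of the point: it is missing relative to the purpose of the secondary objectives, not relative to a stated AHI contrast. The missing AutoEPAP value does not depend on it.
- **Other text may already cover AHI.** The sleep-breathing list is given by example and could include AHI; the comparative phrase closing the SAP's endpoint sentence could be read to govern item (1) as well; and Protocol section 12 compares the modes in general. Against this, SAP section 7 numbers AHI separately and gives it its own manual-only sentence, so a programmer would produce one AHI column. If the comparative phrase does reach item (1), the next sentence of the SAP contradicts it. Protocol section 12 does give some basis for an AutoEPAP summary, but the SAP does not carry it through.
- **It is probably a drafting slip.** Plausible: the same paragraph lists the median twice, and the SAP has two sections numbered 11. That bears on intent, not on what the text instructs.
- **Little depends on it.** The SAP plans SpO₂, PtCO₂ and sleep parameters in both modes, and upper airway obstruction is addressed by the primary ODI4% endpoint. This stands, and it limits the consequence.

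**Conclusion.** The concern holds. As written, SAP section 7 yields an AHI summary for the control mode only, which cannot serve the purpose stated in Protocol section 5.2. This is an instruction that gives the wrong output, not merely a missing detail. It should be corrected before analysis.

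Its size is one descriptive secondary output: two of three summaries are absent for AHI. No hypothesis test, error rate, analysis population or primary conclusion changes. The conclusion rests on reading SAP section 7 literally. Whether the sponsor always meant to tabulate both modes cannot be told from the documents.

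**What to change.** Replace the AHI sentence in SAP section 7 with:

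> Device-measured AHI will be summarised descriptively under AutoEPAP, under manual EPAP, and as the within-subject difference between the two, in the CC population.

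This brings AHI into line with the other secondary endpoints. A 95% confidence interval for the mean paired difference is optional.

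Before making the change, the sponsor should confirm that the Astral device logs AHI in AutoEPAP mode. If it does, the cost is one SAP sentence and two more summary columns, with no new study procedure. If it does not, the SAP should state this and objective 1 in Protocol section 5.2 should be revised, because AHI could not then inform a judgement about AutoEPAP.
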